10.4.3. Other Analyses

The intra-cellular acid parameters and PD parameters collected during the study and after each challenge will be listed for each participant and treatment and summarized descriptively by treatment. If deemed appropriate the dose response relationship at each time point for the change from baseline in key PD parameters will be determined.

PD and biomarker exploratory analyses will be described in the RAP.

It is intended that a population PK model will be built to predict the exposures at the next ascending dose from the currently available PK data.

The population PK and PK/PD analyses and exploratory biomarker analyses may be presented separately from the main clinical study report (CSR).

10.4.4. Interim Analyses

If a decision is made to perform challenges on a previously tested dose (i.e. not evaluate a new dose regimen) in the challenge cohort (Cohort 8), a formal interim statistical analysis will be performed on the completed cohorts in Part A, Part B and Part C of the study once all participants complete Cohort 7 of Part C to aid internal decision making. There will be no changes to the study design or planned number of participants in Cohort 8 as a direct result of the interim analysis.

Dose escalation meetings will also occur after each Period in Part A and after the completion of up to 14 days dosing of each cohort in Part C.

The decision to proceed to the next cohort, and next dose strength to be studied, or to the next study Part, will be made by the DEC based on assessment of safety, plasma

GSK3358699 pharmacokinetic concentrations and target engagement data obtained in all participants at the prior dose level. Individual safety data (AEs, laboratory safety tests, ECGs and vital signs) will be reviewed, according to the DEP.

This study is double blind (sponsor open), where the participant, investigator and site staff will remain blinded to the treatment allocation. Sponsor open refers only to those members of the DEC. Note that Part B will be open label.

The RAP will describe the planned interim analyses in greater detail.

11. **REFERENCES**

Belkina AC. & Denis GV. BET domain co-regulators in obesity, inflammation and cancer. *Nat Rev Cancer*, 2012; 12, 465-77.

Chen H, Yu K-D & Xu G-Z. Association between Variant Y402H in Age-Related Macular Degeneration (AMD) Susceptibility Gene CFH and Treatment Response of AMD: A Meta-Analysis. *PLOS ONE*, 2012; 7, e42464.

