The decision on the dose level of GSK3358699 for the next repeat dose cohort (Cohort 6 onwards) will be made at a DEC meeting following completion of a minimum 14 days dosing in no fewer than 12 participants in the current repeat dose cohort and will be based on:

- assessment of all available safety, tolerability, PK, PD and TE data accumulated from Part A of the study.
- assessment of safety, plasma GSK3358699 PK concentrations and TE data obtained in a minimum of 12 participants in the most recently dosed group of subjects. Individual safety data (AEs, laboratory safety tests, ECGs and vital signs) will be reviewed.
- evaluation of all available safety, tolerability, PK, PD and TE data accumulated from the previous repeat dose cohorts.

As part of this decision making process, the DEC may decide to escalate or de-escalate the dose. Safety, PK and PD stopping criteria will be strictly applied as in Part A of the study. Details of these criteria can be found in Section 8.

Further information on dose decisions / modifications is provided in Section 7.2.

The total duration of the multiple ascending dose phase of Part C, including screening and follow-up, is approximately 10 weeks for each participant in Cohorts 5 - 7.

5.1.3.3. Part C Repeat Dosing Followed by LPS or GM-CSF Challenge with Cantharidin-Induced Blisters Cohort 4 and 8

Upon conclusion of the multiple ascending dose phase of Part C (Cohorts 5 - 7), an additional Cohort (Cohort 8) is planned to be included (Figure 3). This cohort will be comprised of 20 participants, taking part in one repeat dose treatment period.

Participants will be randomised in a 1:1 ratio to receive GSK3358699 or placebo once daily for up to 14 days. The actual duration of dosing will be decided by the DEC and will not exceed 14 consecutive days.

Participants will attend the clinic for outpatient visits, on Day -10 (\pm 3 days), to have control blisters induced on the forearm (0.2% cantharidin) and will have a blister sample taken at a timepoint at approximately 48 hours post-blister induction.

On the final day of dosing, an IV *in vivo* LPS challenge at a dose of 0.75 ng/kg or a 60 μ g/m² GM-CSF challenge as an IV infusion will be administered as per the timepoints detailed in the SoA (Section 2.4.1), followed by blister induction (as described in Section 5.1.1.2 Part A, treatment Period 4).

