The planned doses of GSK3358699 for Periods 1-3 of Part A are as detailed in Section 5.5 and in Table 4. The planned doses may be adjusted as detailed in Section 7.2.

Table 4Example Illustration of Planned Treatments for Dose Escalation in
Part A.

		Treatment Per	riod 1	Treatment Per	riod 2	Treatment Per	riod 3
Cohort 1	N=3	Р		10 mg		35 mg	
	N=3	1 mg		Р		35 mg	
	N=3	1 mg		10mg		Р	
Cohort 2	N=3		Р		20 mg		45 mg
	N=3		3 mg		Р		45 mg
	N=3		3 mg		20 mg		Р

P= Placebo

1-45 mg = GSK3358699

The GSK3358699 dose for the challenge agent treatment Period 4 will be confirmed following completion of the dose escalation treatment Periods 1-3. The GSK3358699 dose for Part B, and the first cohort in Part C will be confirmed following completion of the dose escalation and challenge treatment Periods in Part A. Doses for subsequent cohorts in Part C will be confirmed following completion of the previous Part C cohort at the prior dose level as further detailed in Section 5.5 and Section 7.2.

Table 5	Challenge A	Agents
---------	-------------	--------

Study Treatment Name:	Cantharone (Cantharidin)	LPS	GM-CSF	Intravenous Hydration with saline solution (for LPS only)
Dosage formulation:	Liquid (mixture) Ether (42.8 % W/V), Acetone (36.0 % V/V), Alcohol (14.2 % W/V), Camphor (1.2 % W/V), Cantharidin (0.7 % W/V) Balance (5.1%W/V) mixture of pyroxylin and castor oil	LPS is lyophilized in a 1 microgram vial, formulated in 1% lactose and 0.1% PEG6000.	The vial of lyophilized LEUKINE contains 250 mcg (1.4 × 10 ⁶ IU/vial) sargramostim. The reconstituted lyophilized LEUKINE vial also contain 40 mg/mL mannitol, USP; 10 mg/mL sucrose, NF; and 1.2 mg/mL tromethamine, USP, as excipients.	0.9% Sodium Chloride IV bags.
Unit dose strength(s)/Dos age level(s):	0.7% cantharidin liquid which will be diluted with acetone to 0.2%	0.75 ng/kg (activity 6 EU/ng)	60µg / m²	1L
Route of Administration	Topical	IV	IV infusion	IV
Dosing instructions:	Apply 5 μ l of 0.2 % Cantharidin solution (diluted in acetone) directly onto skin in area of ~ 1 cm ² .	IV injection of 0.75 ng/kg body weight formulated as suspension in normal saline.	Dose calculated by calculating body surface area to give IV infusion dose given over approximately 2 hours.	Administer intravenously at a rate of 250 mL/hr for 4 hours prior to dosing with LPS and 8 hours after dosing with LPS.

Study Treatment Name:	Cantharone (Cantharidin)	LPS	GM-CSF	Intravenous Hydration with saline solution (for LPS only)

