8.1.7. Dose Adjustment/Stopping Pharmacokinetic Criteria

The following dose adjustment / PK stopping criteria will apply:

- If mean cohort exposure exceeds or is predicted to exceed the C_{max} of 42 ng/ml or total daily AUC of 255 ng/ml.h, dose escalation will be stopped.
- Individuals in each cohort will be monitored throughout the study. If 2 or more participants in a given cohort at the same dose level exceed these stopping criteria, dose escalation will be halted.
- If the PK stopping criteria is reached with initial doses, the dose escalation will be stopped. The GSK team will decide based on safety, PK and any available PD

information whether to evaluate any lower doses or repeat doses already evaluated in remaining periods to collect additional safety, PK and PD data.

Throughout all parts of the study, either a population PK model or the results of a noncompartmental analysis will be used to help inform the choice of the next dose level as part of dose escalation discussions. For either approach, it is planned that the 95th percentile for the predicted total daily AUC values will not exceed 1/3 of the mean AUC observed at the cynomolgus monkey NOAEL and the 95th percentile of the predicted C_{max} will not exceed 1/3 of the mean C_{max} observed at the cynomolgus monkey NOAEL.

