- Participants must be informed that their participation is voluntary. Participants or their legally authorized representative will be required to sign a statement of informed consent that meets the requirements of 21 CFR 50, local regulations, ICH guidelines, Health Insurance Portability and Accountability Act (HIPAA) requirements, where applicable, and the IRB/IEC or study centre.
- The medical record must include a statement that written informed consent was obtained before the participant was enrolled in the study and the date the written consent was obtained. The authorized person obtaining the informed consent must also sign the ICF.
- Participants must be re-consented to the most current version of the ICF(s) during their participation in the study.
- A copy of the ICF(s) must be provided to the participant or the participant's legally authorized representative.
- Participants who are rescreened are required to sign a new ICF.

Data Protection

- Participants will be assigned a unique identifier by the sponsor. Any participant records or datasets that are transferred to the sponsor will contain the identifier only; participant names or any information which would make the participant identifiable will not be transferred.
- The participant must be informed that his/her personal study-related data will be used by the sponsor in accordance with local data protection law. The level of disclosure must also be explained to the participant.
- The participant must be informed that his/her medical records may be examined by Clinical Quality Assurance auditors or other authorized personnel appointed by the sponsor, by appropriate IRB/IEC members, and by inspectors from regulatory authorities.

Committees Structure

Dose Escalation Committee

The DEC will make the decision to proceed to the next dose level of GSK3358699 at the end of each single dose (Cohorts 1-2) and repeat dose cohort (Cohorts 4-8); along with making the decision on the dose for Part B of the study and the decision to move into Part C of the study. For details of the information to be considered as part of this decision making process see Section 5.1.

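### Part C, Cohort 6 onwards: Protocol 5.1.3.2 lets the next dose be set on PK from 12 of 18 participants with no minimum on active drug, while 10.4.4 asks for all participants and 7.1 for a completed cohort

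*Protocol*

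**What the plan says.** Four parts of the Protocol bear on when the next Part C dose may be set.

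- **5.1.3.2 (Cohorts 5, 6 and 7).** From Cohort 6 onwards the dose meeting takes place "following completion of a minimum 14 days dosing in no fewer than 12 participants in the current repeat dose cohort". The evidence from that cohort is safety data, "plasma GSK3358699 PK concentrations and TE data obtained in a minimum of 12 participants in the most recently dosed group of subjects". For earlier Part C cohorts the request is wider: "evaluation of all available safety, tolerability, PK, PD and TE data accumulated from the previous repeat dose cohorts". No number of active participants is given.
- **10.4.4 (Interim Analyses).** The meeting is held "after the completion of up to 14 days dosing of each cohort in Part C", and the decision rests on safety, plasma PK and "target engagement data obtained in all participants at the prior dose level".
- **7.1 (Treatments Administered).** "Doses for subsequent cohorts in Part C will be confirmed following completion of the previous Part C cohort at the prior dose level".
- **Appendix 3 (12.3).** The committee decides when each cohort ends, and the reader is referred to Section 5.1 for the information it considers.

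The rule that depends on these data is the PK halt in 8.1.7, with limits of Cmax 42 ng/ml and total daily AUC 255 ng/ml.h: "If 2 or more participants in a given cohort at the same dose level exceed these stopping criteria, dose escalation will be halted". The same section says individuals are monitored against these limits for the whole study. Table 1 gives 18 participants per cohort (9 active, 9 placebo) and an evaluable number of 12, also without a split by arm.

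**The concern.** The halt is a count over the cohort. Only active participants can contribute to it, and a count taken on incomplete active data can only be too low. Section 5.1.3.2, read by itself, allows the committee to find the halt not met and release a higher dose while some active PK is outstanding. Sections 10.4.4 and 7.1, read by themselves, do not. The Protocol does not say which governs, and the one cross-reference, in Appendix 3, points to the section with the lower requirement.

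Data could be outstanding for ordinary reasons: dosing is staggered behind the sentinels, and a replacement participant starts the treatment period from the beginning (5.2). At stake is the exposure of the next cohort to a higher dose when the current dose has already met a halting rule.

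**Working it through.** The plan gives no figure for this rule. Its only stated calculation, the 0.04 to 0.58 interval for one event in six (10.2.1), reproduces as the 2.5% and 97.5% points of Beta(2, 6), 0.037 and 0.579, but has no bearing here.

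**Active participants among 12 of 18.** Inputs: 9 active and 9 placebo (Table 1). The fewest possible is 12 − 9 = 3. If the 12 are a random subset, P(a active) = C(9,a)·C(9,12−a)/C(18,12).

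| a | 3 | 4 | 5 | 6 | 7 | 8 | 9 |
|---|---|---|---|---|---|---|---|
| P | 0.0045 | 0.061 | 0.244 | 0.380 | 0.244 | 0.061 | 0.0045 |

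The mean is 6, and 5 to 7 covers 0.87. Three is allowed but improbable.

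**Chance that a met halt is not yet visible.** Let u be the number of active participants without PK results. Exceeders are assumed equally likely to be among those assayed and those outstanding.

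- Exactly two of nine exceed: unseen = 1 − C(9−u,2)/C(9,2).
- Exactly three exceed: the halt is unseen if at most one is among those assayed. For u = 2 this is C(2,2)·C(7,1)/C(9,3) = 7/84. For u = 3 it is [C(3,3) + C(3,2)·C(6,1)]/84 = 19/84.

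| u | Two exceed | Three exceed |
|---|---|---|
| 0 | 0% | 0% |
| 1 | 1 − 28/36 = 22% | 0% |
| 2 | 1 − 21/36 = 42% | 8% |
| 3 | 1 − 15/36 = 58% | 23% |

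**How likely two exceeders are.** Inputs: predicted Cmax and AUC from Table 2 (5.5.1), divided by 42 and 255. The documents give no between-participant CV; I assume 30% to 50%. Treat exposure as lognormal with the prediction as median and σ = √ln(1 + CV²). Let p be the larger of the Cmax and AUC exceedance probabilities, and take the binomial chance of two or more among nine.

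| Dose | Cmax/42 | AUC/255 | CV 30% | CV 50% |
|---|---|---|---|---|
| 10 mg | 9/42 = 0.21 | 57/255 = 0.22 | <0.01% | <0.01% |
| 20 mg | 19/42 = 0.45 | 113/255 = 0.44 | 0.04% | 6% |
| 35 mg | 32/42 = 0.76 | 199/255 = 0.78 | 56% | 80% |

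**What Day 1 already shows.** Every Cohort 5–7 participant has a PK profile to 24 h on Day 1 (schedule 2.3). With the predicted half-life of about 3 h (5.4), accumulation under daily dosing is 1/(1 − 2⁻⁸) = 1.004. A participant above the limit on Day 14 would therefore usually be above it on Day 1, and u can be zero without everyone completing 14 days, provided the Day 1 samples have been assayed.

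**The case against.** The strongest reply is that the sections are cumulative. Section 5.1.3.2 uses the language of a floor, and a floor does not permit the rest of the data to be ignored. A decision taken at cohort end, on everyone's data, with at least 12 having had 14 days' dosing, satisfies all four texts. The number 12 equals the evaluable number in Table 1, as 6 of 9 does in Part A, which suggests an allowance for dropout. This reading is reasonable and probably intended, but the Protocol does not state it.

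Three stronger readings are tempting, and the documents do not support them.

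- A reader might infer that no text requires PK from all active participants. Section 10.4.4 does; the difficulty is that 5.1.3.2 asks for less and is where Appendix 3 points.
- A reader might infer that a second exceeder could be missed for good. Monitoring under 8.1.7 continues, so a late result still halts further escalation. The exposure is limited to the one dose already released.
- A reader might take a random 12 of 18, with no PK from the other six, as the expected case. Averaged over the split above, that gives 57% unseen for two exceeders and 25% for three. It supposes that six dosed participants supply no results, despite their Day 1 samples and contrary to 10.4.4 and 7.1. It is an upper bound only.

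It is also fair to say that the Dose Escalation Plan, which covers the accuracy and completeness of the data used, may settle the matter. It is not among the documents. The mean-exposure halt, the 95th-percentile limit and the Part A dose ceiling apply in any case.

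**Conclusion.** The inconsistency is real and minor. Three sections state different data requirements for one dose decision, and the weakest can be followed as written. The consequence is bounded: a next dose might be released before a second exceeder is seen, with probability 22%, 42% or 58% given exactly two exceeders and one, two or three active results outstanding. Those figures are conditional on two exceeders. On the assumed CVs that condition is remote at 10 mg and likely only near the exposure limit; the dose table also takes pre-study predictions as medians, whereas a real Cohort 6 decision would have used observed PK.

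The rule never released a dose. The SAP (2.3 and 5.2) records that only Cohorts 4 and 5 were dosed in Part C, both at 10 mg. Nobody should infer that a participant was exposed because of this gap.

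**What to change.** State one Part C rule in 5.1.3.2, 7.1 and 10.4.4, and mirror it in the Dose Escalation Plan:

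- Keep 12 as the minimum number completing 14 days' dosing.
- Before the two-participant PK halt is declared not met and the next dose released, require available PK results from every dosed active participant: at least the Day 1 profile, plus Day 14 where reached. Include early withdrawals who gave samples.

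The unblinded committee members include the statistician and the pharmacokineticist (Appendix 3), so active participants can be identified without unblinding the site. As a consistency edit only, align the 10.4.4 wording with the Part A minimum of six in 5.1.1.1.

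The cost is wording in three sections and possibly a short wait for outstanding assays; turnaround time is not given in the documents.

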12. APPENDICES

12.1. Appendix 1: Abbreviations and Trademarks

AEAdverse EventALPAlkaline PhosphataseALTAlanine AminotransferaseAMDAge-related Macular DegenerationAPIActive Pharmaceutical IngredientAPTTActivated Partial Thromboplastin TimeASTAspartate AminotransferaseAUCArea Under the CurveBETBromodomain and Extra Terminal domainBMIBody Mass IndexBPBlood PressureBSABody Surface AreaBUNBlood Urea NitrogenCDCluster of DifferentiationCDERCenter for Drug Evaluation and Research	Abbreviations				
ALTAlanine AminotransferaseAMDAge-related Macular DegenerationAPIActive Pharmaceutical IngredientAPTTActivated Partial Thromboplastin TimeASTAspartate AminotransferaseAUCArea Under the CurveBETBromodomain and Extra Terminal domainBMIBody Mass IndexBPBlood PressureBSABody Surface AreaBUNBlood Urea NitrogenCDCluster of Differentiation	AE	Adverse Event			
AMDAge-related Macular DegenerationAPIActive Pharmaceutical IngredientAPTTActivated Partial Thromboplastin TimeASTAspartate AminotransferaseAUCArea Under the CurveBETBromodomain and Extra Terminal domainBMIBody Mass IndexBPBlood PressureBSABody Surface AreaBUNBlood Urea NitrogenCDCluster of Differentiation	ALP	Alkaline Phosphatase			
APIActive Pharmaceutical IngredientAPTTActivated Partial Thromboplastin TimeASTAspartate AminotransferaseAUCArea Under the CurveBETBromodomain and Extra Terminal domainBMIBody Mass IndexBPBlood PressureBSABody Surface AreaBUNBlood Urea NitrogenCDCluster of Differentiation	ALT				
APIActive Pharmaceutical IngredientAPTTActivated Partial Thromboplastin TimeASTAspartate AminotransferaseAUCArea Under the CurveBETBromodomain and Extra Terminal domainBMIBody Mass IndexBPBlood PressureBSABody Surface AreaBUNBlood Urea NitrogenCDCluster of Differentiation	AMD				
APTTActivated Partial Thromboplastin TimeASTAspartate AminotransferaseAUCArea Under the CurveBETBromodomain and Extra Terminal domainBMIBody Mass IndexBPBlood PressureBSABody Surface AreaBUNBlood Urea NitrogenCDCluster of Differentiation	API	Active Pharmaceutical Ingredient			
AUCArea Under the CurveBETBromodomain and Extra Terminal domainBMIBody Mass IndexBPBlood PressureBSABody Surface AreaBUNBlood Urea NitrogenCDCluster of Differentiation	APTT				
BETBromodomain and Extra Terminal domainBMIBody Mass IndexBPBlood PressureBSABody Surface AreaBUNBlood Urea NitrogenCDCluster of Differentiation	AST	Aspartate Aminotransferase			
BMIBody Mass IndexBPBlood PressureBSABody Surface AreaBUNBlood Urea NitrogenCDCluster of Differentiation	AUC				
BPBlood PressureBSABody Surface AreaBUNBlood Urea NitrogenCDCluster of Differentiation	BET				
BSABody Surface AreaBUNBlood Urea NitrogenCDCluster of Differentiation	BMI				
BUN Blood Urea Nitrogen CD Cluster of Differentiation	BP				
CD Cluster of Differentiation	BSA				
CD Cluster of Differentiation	BUN	Blood Urea Nitrogen			
CDER Center for Drug Evaluation and Research	CD				
	CDER	Center for Drug Evaluation and Research			
cDNA Complementary DNA	cDNA				
CES Carboxyesterase	CES	Carboxyesterase			
CFR Code of Federal Regulations	CFR	Code of Federal Regulations			
CI Confidence Interval	CI	* *			
CIOMS Council for International Organizations of Medical Sciences	CIOMS	Council for International Organizations of Medical Sciences			
C _{max} Maximum Concentration	C _{max}				
CK Creatine Kinase	СК	Creatine Kinase			
CONSORT Consolidated Standards of Reporting Trials	CONSORT	Consolidated Standards of Reporting Trials			
COPD Chronic Obstructive Pulmonary Disease	COPD				
CPK Creatine Phosphokinase	СРК				
(e)CRF (electronic) Case Report Form	(e)CRF	(electronic) Case Report Form			
CRP C-reactive protein	CRP	C-reactive protein			
CSR Clinical Study Report	CSR				
CTCAE Common Terminology Criteria for Adverse Events	CTCAE	Common Terminology Criteria for Adverse Events			
CV Cardiovascular	CV				
CYP3A4 Cytochrome P450 3A4	CYP3A4				
DDI Drug Interaction	DDI	Drug Interaction			
DEC Dose Escalation Committee	DEC	Dose Escalation Committee			
DEP Dose Escalation Plan	DEP	Dose Escalation Plan			
DNA Deoxyribonucleic Acid	DNA	Deoxyribonucleic Acid			
ECG Electrocardiogram	ECG	Electrocardiogram			
EDTA Ethylenediaminepentaacetic acid	EDTA	Ethylenediaminepentaacetic acid			
E _{max} Maximum Effect Possible	E _{max}				
ESM Esterase Sensitive Motif		Esterase Sensitive Motif			
EU European Union					

FDA	Food and Drug Administration				
FTIH	First Time In Human				
GCP	Good Clinical Practice				
GCSP	Global Clinical Safety and Pharmacovigilance				
GGT	Gamma-glutamyl transferase				
GI	Gastrointestinal				
GM-CSF	Granulocyte-Macrophage Colony-Stimulating Factor				
GSK	GlaxoSmithKline				
HED	Human Estimated Dose				
HIPAA	Health Insurance Portability and Accountability Act				
HIV	Human Immunodeficiency Virus				
HLA-DR	Human Leukocyte Antigen - antigen D Related				
HPLC	High Performance Liquid Chromatography				
HR	Heart Rate				
IB	Investigator's Brochure				
IBD	Inflammatory Bowel Disease				
IC ₅₀	Half Maximal Inhibitory Concentration				
ICF	Informed Consent Form				
ICH	International Conference on Harmonisation				
IG	Immunoglobulin				
IL	Interleukin				
IMP	Investigational Medicinal Product				
IMPD	Investigational Medicinal Product Dossier				
INR	International Normalized Ratio				
IP	Interferon gamma-induced Protein				
IUD	Intra-Uterine Device				
IUS	Intra-Uterine hormone releasing System				
IV	Intravenous				
IRB/IEC	Institutional Review Boards /Independent Ethics Committees				
LDH	Lactose Dehydrogenase				
LPS	Lipopolysaccharide				
MABEL	Minimum Anticipated Biological Effect Level				
MCH	Mean Corpuscular Hemoglobin				
MCP	Monocyte chemoattractant protein				
MCV	Mean Corpuscular volume				
MDC	Macrophage-Derived Chemokine				
MHRA	Medicines and Healthcare Products Regulatory Agency				
MMP	Matrix Metallopeptidase				
MSDS	Material Safety Data Sheet				
NOAEL	No Observed Adverse Effect Level				
NOEL	No Observed Effect Level				
PBO	Placebo				
PBPK	Physiologically Based Pharmacokinetic				
PD	Pharmacodynamics				
PK	Pharmacokinetics				

PT	Prothrombin Time				
QD	Once Daily				
QTc	Electrocardiogram QT interval corrected for heart rate				
QTcF	Electrocardiogram QT interval corrected for heart rate using Fridericia's				
	formula				
RA	Rheumatoid Arthritis				
RAP	Reporting Analysis Plan				
RBC	Red Blood Cell				
RDW	Red cell Distribution Width				
RNA	Ribo Nucleic Acid				
Ro	Accumulation Ration				
Rs	Plasma steady state ratio				
SAD	Single Ascending Dose				
SAE	Serious Adverse Event				
SD	Standard Deviation				
SoA	Schedule of Activities				
SGOT	Serum Glutamic Oxaloacetic Transaminase				
SGPT	Serum Glutamic Pyruvic Transaminase				
SNP	Single Nucleotide Polymorphism				
SPF	Sun Protection Factor				
SRM	Study Reference Manual				
SST	Serum-Separating Tube				
SUSAR	Suspected Unexpected Serious Adverse Reactions				
TARC	Thymus and Activation Regulated Chemokine				
TBC	To Be Confirmed				
TE	Target Engagement				
TGF	Transforming Growth Factor				
T _{max}	Time to C _{max}				
TNF	Tumour Necrosis Factor				
ULN	Upper limit of normal				
UVA/B	Ultra Violet A/B				
WBC	White Blood Cell				
WCC	White Cell Count				

Trademark Information

Trademarks of the GlaxoSmithKline group of companies	
• • •	
NONE	

Trademarks not owned by the GlaxoSmithKline group of companies

Cantharone

Leukine

